13. Vital signs will be assessed prior to treatment as well as approximately 5 and 60 minutes post dose (after last injection) at the first 2 dosing visits (V2, V3).
14. Blood samples should be taken after patient has fasted for at least 8 hours prior (except screening visit). If not fasted mark on laboratory requisition.
15. Patients that terminate trial medication early should remain in the trial and complete all remaining Treatment Period visits and, FU1 and FU2 visits. Termination of trial medication eCRF should be completed and end of study registered as a non-completer in IRT. Refer to [Section 6.2.3](#) for details and further instruction if patient cannot or will not continue in the trial.
16. Tender and swollen joint counts (TJC/SJC) and Disease Activity Score (DAS28) will be done at **selected sites for confirmed psoriatic arthritis patients** (See [Appendix 10.6](#))
17. The patient will be switched to Flow Chart 2 if relapse occurs between Week 32 through Week 70 (inclusive). The R1 visit from the Flowchart 2 must be conducted instead of the current scheduled or unscheduled visit. See also [Flow Chart 2](#) and [Sections 3.1](#) and [6.2.2](#).
18. The patient will be switched to Flow Chart 3 if they relapse after week 70 through to week 82 (inclusive). The R1 visit from Flowchart 3 must be conducted instead of the current scheduled or unscheduled visit. See also [Flow Chart 3](#) and [Sections 3.1](#) and [6.2.2](#).
19. History for psoriatic arthritis is done on **all patients at all sites**
20. For patients who discontinue early, vital status should be collected every 12 months after discontinuation up to the original planned EOO.
21. Patients relapsing after Week 82 through Week 88 will immediately follow EOT procedures per Flow Chart 1 (see also [Section 3.1](#) and [6.2.2](#)).
22. For patients re-randomized at Week 28 continuing in the double blind treatment portion of the study, assessment of relapse is defined as having an $sPGA \geq 3$. If the $sPGA$ is ≥ 3 , the result is entered into IRT and IRT will immediately dispense open label BI 655066.
23. Infection Testing: Note that at the Screening Visit (or prior to randomization) only TB testing is required. See [Section 5.3.3.1](#) for a complete list of testing required.

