5.3.2 Vital Signs

Vital sign evaluations will be performed at every visit as shown in the Flow Charts and includes temperature, pulse rate, systolic/diastolic blood pressure and respiratory rate. Respiratory rate, pulse rate, and blood pressure will be measured after patients have been sitting comfortably for at least five minutes. Measurement of vital signs should precede blood sampling to avoid the impact of blood sampling on the vital measurements. At dosing visits vital sign evaluations will be performed pre-dose. In addition at Visit 2 and Visit 3 vital sign evaluations will be taken at approximately 5 minutes post-dose (5 minutes after last injection) and approximately 60 minutes post-dose (60 minutes after last injection).

Patients should be closely monitored for signs and symptoms of hypersensitivity reactions for approximately 2 hours after the last injection at Visit 2 and for approximately 1 hour after the

last injection at all other visits where drug is administered. Hypersensitivity reactions should be treated according to medical standards. Pre-medications for further injections might be considered and will be agreed on between investigator and BI clinical monitor.

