6.0 Analysis Conventions

Definition of Baseline

The last non-missing measure collected on or before the date of the first dose of study drug injection will be used as Baseline for summary of demographics and disease characteristics, efficacy analyses, and safety analyses in each period, with the exception that:

- The last evaluation on or prior to the first dose date of risankizumab will be used for the safety analyses for Safety_ARM2 and ALL_RZB populations.
- For all vital sign assessments, only assessments prior to first dose time will be considered, since vital signs are to be assessed both pre- and post-dose in some visits.

For subjects who are randomized but do not take any study drug during the study, the last non-missing measurement collected on or before the date of randomization will be used as Baseline.

Definition of Final Observation (Applicable to Safety Analyses)

Final observation for the Part A1 is defined as:

- The last non-missing observation collected within 105 days following the last dose of study drug in Part A1, for subjects who were not dosed in Part A2.
- The last non-missing observation collected on or before the first dose date of study drug on or after Week 16 and within 105 days following the last dose of study drug in Part A1, for subjects who were dosed in Part A2. For vital sign assessments, only assessments prior to the first dose of study drug injection in Part A2 will be included in the analysis for Part A1.

Final observation for the Part A2 is defined as:

- The last non-missing observation collected within 105 days following the Week 16 dose of study drug in Part A2, for subjects who were not dosed in Part B.
- The last non-missing observation collected on or before the first dose date of Part B, or within 105 days following the last dose of study drug in Part A2, whichever comes first, for subjects who were dosed in Part B. For vital sign assessments, only assessments prior to the first dose of study drug injection in Part B will be included in the analysis for Part A2.

Final observation in Part B is defined as the last non-missing observation collected within 105 days following the last dose of study drug, and on or prior to the date first dose of retreatment with risankizumab for relapsed subjects, with the following exception:

For vital sign assessments, only assessments prior to the first dose of retreatment will be included in the analysis for Part B.

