Final observation in the retreatment period is defined as the last non-missing observation collected within 105 days after the last dose of retreatment with risankizumab.

Final observation in the entire study is defined as the last non-missing observation collected within 105 days after the last dose of study drug.

Definition of Rx Days (Days Relative to the Date of First Dose of Study Drug)

Rx days are calculated for each time point relative to the date of first dose of study drug. They are defined as the number of days between the day of the first dose of study drug and the specific time point. Rx days are negative values when the time point of interest is prior to the first study drug dose day. Rx days are positive values when the time point of interest is on or after the first study drug dose day. The day of the first dose of study drug is defined as Rx Day 1, while the day prior to the first study drug dose is defined as Rx Day –1 (there is no Rx Day 0).

For analysis in each Part (A1, A2, or B), the Rx Day is calculated relative to the first dose of study drug in the specific study Part. For analysis across Part A2 and Part B, the Rx days are calculated relative to the date of first dose of risankizumab injection in Part A2.

Definition of Analysis Windows

All time points and corresponding time windows are defined based on Rx Days.

For efficacy analyses, local tolerability, ECG, laboratory parameters, and vital sign variables, analysis windows are constructed using the following algorithm:

- Determine the nominal Rx day for each visit (e.g., Week 4 [4 weeks after Baseline visit] equals Rx Day 29).
- In order to include all post baseline data, the first post-baseline interval starts on the first day after the first dose of study drug (Rx Day 2).
- Determine the window around a specific nominal Rx day by adding or subtracting half of the interval between adjacent visits (e.g., days between Week 2 and Week 4 is 14). The threshold between adjacent visits is determined by splitting the interval evenly between the visits. If the resulting split is between Rx days, then the threshold is determined as the midpoint between the adjacent visits. If the resulting split is on an Rx day, then the threshold is determined as being between that Rx day and the Rx day prior to it (e.g., the split between Week 2 and Week 4 would be between Rx Days 22 and 23).

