- If more than one assessment is included in a time window the assessment closest to the nominal day will be used. If there are two observations equidistant to the nominal day, the one after the nominal day will be used in analyses. If more than one assessment is included on the same day, then the worst assessment on that day will be used in analyses, except those specified in Section 11.0.

The protocol specified visits and corresponding time windows used in the efficacy analyses, local tolerability, ECG, laboratory parameters, and vital sign variables, are

presented in the following Table 2, Table 3, Table 4, Table 5, Table 6, Table 7, Table 8, Table 9, Table 10, Table 11, Table 12, Table 13, Table 14, Table 15 and Table 16.

Table 2. Visit Windows for Analysis of PASI, sPGA, Local Tolerability, and Vital Signs in Part A1 (ITT_A1/PP_A1/Safety_A1 Populations)

Window Label	Target Day	Interval
Baseline	1	$\leq 1^a$
Week 4	29	[2, 43]
Week 8	57	[44, 71]
Week 12	85	[72, 99]
Week 16	113	[100, 127 ^b]

Rx Day calculated relative to first dose date of study drug. For subjects randomized but not dosed, Rx Day calculated relative to Randomization.

- a. There is no baseline for local tolerability measurements. If time is collected in vital signs, restrict to records prior to the first dose of study drug.
- b. The minimum of upper bound and first dose date of study drug on or after Week 16 (and within 105 days of last dose for safety analyses). If time is collected in vital signs, restrict to records prior to the first dose of study drug on or after Week 16.

Table 3. Visit Windows for Analysis of DLQI in Part A1 (ITT_A1/PP_A1 Populations)

Window Label	Target Day	Interval
Baseline	1	≤ 1
Week 12	85	[2, 99]
Week 16	113	[100, 127 ^a]

Rx Day calculated relative to first dose date of study drug. For subjects randomized but not dosed, Rx Day calculated relative to Randomization.

- a. The minimum of upper bound and first dose date of study drug on or after Week 16.

Table 4. Visit Windows for Analysis of Safety Laboratory Tests and ECG in Part A1 (Safety_A1 Population)

Window Label	Target Day	Interval
Baseline	1	≤ 1
Week 4	29	[2, 71]
Week 16	113	[72, 155 ^a]

Rx Day calculated relative to first dose date of study drug. For subjects randomized but not dosed, Rx Day calculated relative to Randomization.

a. The minimum of upper bound and first dose date of study drug on or after Week 16 (and within 105 days of last dose for safety analyses).

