Table 12. Visit Windows for Analysis of Other Efficacy Endpoints Collected at Week 28, 52, 76, and 104 in Part A2 and B (ITT_ARM2 Population)

Window Label	Target Day	Interval
Entry of A2	1	≤ 1
Week 28	85	[2, 169]
Week 52	253	[170, 337]
Week 76	421	[338, 519]
Week 104	617	[520, 715]

Rx Day calculated relative to first dose date of risankizumab.

Table 13. Visit Windows for Analysis of PASI and sPGA During Retreatment with Risankizumab (ITT_B_PBO_RT/ITT_B_RZB_RT Populations)

Window Label	Target Day	Interval
Entry of RTS	1	≤ 1
Week 8R	57	[2, 85]
Week 16R	113	≥ 86

Rx Day calculated relative to first dose date of retreatment with risankizumab.

Table 14. Visit Windows for Analysis of Other Efficacy Variables Only Collected at EOT and EOO Visits During Retreatment with Risankizumab (ITT_B_PBO_RT/ITT_B_RZB_RT Populations)

Window Label	Target Day	Interval
Entry of RTS	1	≤ 1
Week 16R	113	≥ 2

Rx Day calculated relative to first dose date of retreatment with risankizumab.

Table 15. Visit Windows for Analysis of Vital Signs and Local Tolerability in the ALL_RZB Population

Window Label	Target Day	Interval
Baseline	1	$\leq 1^a$
Week 4	29	[2, 43]
Week 8	57	[44, 71]
Week 12	85	[72, 99]
Week 16	113	[100, 155]
Week 28	197	[156, 239]
Week 40	281	[240, 323]
Week 52	365	[324, 407]
Week 64	449	[408, 491]
Week 76	533	[492, 575]
Week 88	617	[576, 673]
Week 104	729	[674, 785 ^b]

Rx Day calculated relative to first dose date of risankizumab.

- a. Local tolerability not measured at Baseline and at Week 104. If time is collected in vital signs, restrict to records prior to the first dose of risankizumab.
- b. The minimum of upper bound and within 105 days of last dose of risankizumab.

Table 16. Visit Windows for Analysis of Safety Laboratory Tests and ECG in the ALL_RZB Population

Window Label	Target Day	Interval
Baseline	1	≤ 1
Week 4	29	[2, 71]
Week 16	113	[72, 155]
Week 28	197	[156, 239]
Week 40	281	[240, 323]
Week 52	365	[324, 407]
Week 64	449	[408, 491]
Week 76	533	[492, 575]
Week 88	617	[576, 673]
Week 104	729	[674, 785 ^a]

Rx Day calculated relative to first dose date of risankizumab.

a. The minimum of upper bound and within 105 days of last dose of risankizumab.

The time windows specified in [Table 17](#), [Table 18](#), [Table 19](#), [Table 20](#), [Table 21](#) and [Table 22](#) will be used for the summary of study drug injections of each period.

Table 17. Visit Windows for Summary of Study Drug Injections for Part A1

Window Label	Target Day	Interval

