Table 26. Criteria for Potentially Clinically Important Hematology Values

Hematology Variables	Units	Definition of Potentially Clinically Important Current (Version 4) Grade 3 or Greater	
		Very Low	
Hemoglobin	g/dL	< 8.0	
Platelets count	10 ⁹ /L	< 50.0	
WBC count	10 ⁹ /L	< 2.0	
Neutrophils	10 ⁹ /L	< 1.0	
Lymphocytes	10 ⁹ /L	< 0.5	

Note: A post baseline value must be more extreme than the baseline value to be considered a potentially clinically important finding.

A separate listing will be provided that presents all of the subjects and values that are NCI CTCAE toxicity grade 3 or above. For each of these subjects, the whole course of the respective parameter will be listed. The NCI CTCAE grading is shown in [Table 27](#) below:

Table 27. NCI CTCAE Grading

Test	Grade 1	Grade 2	Grade 3	Grade 4
SGPT/ALT increased	> ULN – 3.0 × ULN	> 3.0 – 5.0 × ULN	> 5.0 – 20.0 × ULN	> 20.0 × ULN
SGOT/AST increased	> ULN – 3.0 × ULN	> 3.0 – 5.0 × ULN	> 5.0 – 20.0 × ULN	> 20.0 × ULN
GGT increased	> ULN – 2.5 × ULN	> 2.5 – 5.0 × ULN	> 5.0 – 20.0 × ULN	> 20.0 × ULN
ALP increased	> ULN – 3.0 × ULN	> 3.0 – 5.0 × ULN	> 5.0 – 20.0 × ULN	> 20.0 × ULN
TBL increased	> ULN – 1.5 × ULN	> 1.5 – 3.0 × ULN	> 3.0 – 10.0 × ULN	> 10.0 × ULN
Creatinine increased	> ULN – 1.5 × ULN	> 1.5 – 3.0 × ULN	> 3.0 – 6.0 × ULN	> 6.0 × ULN
CPK increased	> ULN – 2.5 × ULN	> 2.5 – 5.0 × ULN	> 5.0 – 10.0 × ULN	> 10.0 × ULN
Hemoglobin decreased	< LLN – 100.0 g/L	< 100.0 – 80.0 g/L		< 80.0
Neutrophil count decreased	< LLN – 1.5 × 10 ⁹ /L	< 1.5 – 1.0 × 10 ⁹ /L	< 1.0 – 0.5 × 10 ⁹ /L	< 0.5 × 10 ⁹ /L
WBC decreased	< LLN – 3.0 × 10 ⁹ /L	< 3.0 – 2.0 × 10 ⁹ /L	< 2.0 – 1.0 × 10 ⁹ /L	< 1.0 × 10 ⁹ /L
Lymphocyte count decreased	< LLN – 0.8 × 10 ⁹ /L	< 0.8 – 0.5 × 10 ⁹ /L	< 0.5 – 0.2 × 10 ⁹ /L	< 0.2 × 10 ⁹ /L

If there are multiple post-baseline measurements on the same day, the worst value will be used.

Liver Function Tests

Additional summaries will be presented for liver function tests including ALT or serum glutamic-pyruvic transaminase (SGPT), AST or serum glutamic-oxaloacetic transaminase (SGOT), alkaline phosphatase, and total bilirubin. Each laboratory value will be categorized as follows:

- $< 1.5 \times \text{ULN}$
- $\geq 1.5 \times \text{ULN} - < 3.0 \times \text{ULN}$
- $\geq 3.0 \times \text{ULN} - < 5.0 \times \text{ULN}$
- $\geq 5.0 \times \text{ULN} - < 10.0 \times \text{ULN}$
- $\geq 10.0 \times \text{ULN} - < 20.0 \times \text{ULN}$
- $\geq 20.0 \times \text{ULN}$

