11.4.2 Statistical Methods

Changes from Baseline to each visit and to the final value in vital sign parameters will be summarized with the mean, standard deviation and median. The Baseline and final value means will also be presented for subjects who have both the Baseline and final values (see Section 6.0 for the definition of Baseline and final values).

For baseline, if there are multiple measurements on the same day, the last measurement prior to the first dose of study drug will be used as the Baseline vital sign value. If there are multiple post-baseline measurements on the same day, average value will be used.

For systolic blood pressure, diastolic blood pressure and pulse, a listing of all subjects with any vital sign value meeting criteria for potentially clinically important values will be provided. For each of these subjects, the whole course of the respective parameter will be listed. The number and percentage of subjects who have at least one value meeting criteria for potentially clinically important values will be provided for each selected vital sign parameter.

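### The vital signs timed at 5 and 60 minutes after injection have no summary by time after dose: the by-visit tables drop them on Day 1 and average them with the pre-dose reading at Week 4, and the SAP does not say whether Table 28 uses averaged values.

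*SAP*

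**What the plan says.** **Collection.** Protocol Flow Chart 1, footnote 13: "Vital signs will be assessed prior to treatment as well as approximately 5 and 60 minutes post dose (after last injection", at the first two dosing visits. Protocol 5.3.2 repeats this: "In addition at Visit 2 and Visit 3 vital sign evaluations will be taken at approximately 5 minutes post-dose", and again at about 60 minutes. At other dosing visits vital signs are pre-dose only.

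**Baseline and windows.** SAP 6.0 restricts baseline: "For all vital sign assessments, only assessments prior to first dose time will be considered". Table 2, footnote a, repeats the restriction for Part A1 ("If time is collected in vital signs, restrict to records prior to the first dose of study drug"), and Table 15, footnote a, does so for ALL_RZB ("If time is collected in vital signs, restrict to records prior to the first dose of risankizumab"). SAP 6.0 also says that "the first post-baseline interval starts on the first day after the first dose of study drug (Rx Day 2"). In both tables the Week 4 window is Rx Days 2 to 43, with target day 29.

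**Several readings on one day.** The default in SAP 6.0 is the worst assessment of the day, unless Section 11 specifies otherwise. For vital signs, SAP 11.4.2 does so: "If there are multiple post-baseline measurements on the same day, average value will be used".

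**Outputs.** SAP 11.4.2 plans change from baseline by visit and to the final value. For systolic pressure, diastolic pressure and pulse it also plans a listing of every subject with any value that meets Table 28, and the number and percentage with at least one such value. No output is organised by minutes after dose.

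**The concern.** These are the trial's only scheduled vital signs timed after an injection. They come at the first two exposures, while the arms are still randomised against placebo. Arm 2's first active dose, at Week 16, has no post-dose set. Any between-arm estimate of acute response in blood pressure, pulse, temperature or respiratory rate has to come from Visits 2 and 3.

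The by-visit rules do not use the readings for that purpose. The first-dose readings are left out, and the second-dose readings are merged with a pre-dose reading that is not a response to that injection. The Week 4 figure then measures neither the steady change since baseline nor the acute change after the dose. What is at stake is the descriptive account of acute tolerability; no efficacy conclusion is affected.

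**Working it through.** The plan states no figure to reproduce. The check assigns each reading to a window, works out what averaging does, and then applies Table 28.

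**1. Window membership (SAP Tables 2 and 15)**

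| Reading | Rx Day | By-visit window |
|---|---|---|
| Visit 2 pre-dose | 1 | Baseline |
| Visit 2, 5 and 60 minutes | 1 | None: baseline is pre-dose only and the next window opens on Day 2 |
| Visit 3 pre-dose, 5 and 60 minutes | about 29 | Week 4 (Days 2 to 43), averaged |

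The table footnotes apply only if a time was collected, but the baseline rule in 6.0 carries no such condition, and a Day 1 record cannot enter a window that opens on Day 2. With about 500 patients planned, up to 2 × 500 = 1,000 Day 1 post-dose sets have no by-visit place.

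**2. Effect of averaging at Week 4**

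Let c be the change from baseline in the Week 4 pre-dose reading, and d5 and d60 the further changes at 5 and 60 minutes. The value reported for the visit is

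[c + (c + d5) + (c + d60)] / 3 = c + (d5 + d60)/3.

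- Change d at 5 minutes only: it adds d/3.
- Change d at both post-dose times: it adds 2d/3.

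For example, a group mean fall of 15 mmHg (assumed) would show as 15/3 = 5 if seen only at 5 minutes, or 2 × 15/3 = 10 if seen at both times.

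**3. Table 28 under the two readings of 11.4.2**

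The low systolic criterion is 90 mmHg or less with a fall of at least 20 mmHg. The values below are assumed, with baseline and Week 4 pre-dose both at 120.

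| Pre / 5 min / 60 min | Mean | Change of mean | Lowest reading (change) | Any single reading meets | Mean meets |
|---|---|---|---|---|---|
| 120 / 85 / 120 | 325/3 = 108.3 | −11.7 | 85 (−35) | Yes | No |
| 120 / 85 / 85 | 290/3 = 96.7 | −23.3 | 85 (−35) | Yes | No |

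If averaging governed this output, a pre-dose value b would need a 5-minute reading of at most 270 − 2b (60-minute reading back at b), or both post-dose readings at most (270 − b)/2:

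| b | 5-minute reading alone | Both post-dose readings |
|---|---|---|
| 110 | 50 | 80 |
| 120 | 30 | 75 |
| 130 | 10 | 70 |
| 140 | not reachable (−10) | 65 |

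On Day 1 the pre-dose reading is the baseline, so only the two post-dose readings would be averaged: 85 and 120 give 205/2 = 102.5, which also misses the criterion. If individual readings are used, the 85 is captured in every case. The output therefore depends on a choice that the SAP does not state.

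**The case against.** A reader might infer that an acute change after injection cannot show anywhere, or that a value meeting Table 28 would be reported as normal. The documents do not support that.

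- **Listing and count.** Section 11.4.2 words both in terms of any value or at least one value and ties neither to a window. Read literally, they capture a single qualifying 5-minute reading, including one on Day 1.
- **Place of the averaging sentence.** It stands in the paragraph on baseline and same-day values, before the Table 28 paragraph. If it governs only the means, the worst-value default in 6.0 would apply to Table 28.
- **Laboratory parallel.** SAP 11.3.2 also averages same-day values for change from baseline and keeps the worst for toxicity grading ("If there are multiple post-baseline measurements on the same day, the worst value will be used").
- **Adverse events.** Patients are watched for hypersensitivity for about 2 hours after the Visit 2 injection and about 1 hour after later ones. Vital-sign changes judged clinically relevant are recorded as adverse events. Hypersensitivity and anaphylactic reaction are prespecified areas of safety interest.
- **Scope.** Protocol 7.3.4 calls the safety analyses generally descriptive and promises no summary by minutes after dose. The documents state no expected acute effect.

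All of this stands against the stronger reading, and it narrows the point without removing it. A threshold listing cannot show a mean or sub-threshold shift between arms. The adverse event route rests on the investigator's judgement. Table 28 has no temperature or respiratory rate criteria, so for these only the averaged by-visit summary and adverse event reports remain. The laboratory section assigns a same-day rule to each output; 11.4.2 gives one unqualified post-baseline rule, so two programmers could produce different Table 28 counts.

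**Conclusion.** The point holds for the by-visit summaries. Day 1 post-dose readings enter none of them. At Week 4 an acute change is diluted to one third if present only at 5 minutes, or two thirds if present equally at both times. These fractions follow from the averaging rule and assume that all three readings are available and share one date. The blood pressure values in the working are assumed, and nothing in the documents says that an acute effect is expected.

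For Table 28 the finding is an ambiguity, not a loss. The more natural reading keeps individual values, but the SAP should say so, because under the other reading a single 85 mmHg would go uncounted. The overall consequence is limited to two visits and to descriptive safety. It is worth correcting because these are the only placebo-controlled readings of their kind and the correction costs almost nothing.

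**What to change.** Amend SAP 11.4.2 in three places:

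1. Summarise the 5- and 60-minute readings at Visits 2 and 3 as change from the same visit's pre-dose value, by nominal time and by arm in Safety_A1, for all vital signs recorded at those times.
2. Use only the pre-dose reading as the Week 4 visit value, so that it is comparable with the other visits.
3. State that Table 28 is applied to individual, unaveraged readings, including those taken after the dose on Day 1.

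The cost is a few sentences of SAP wording and one extra descriptive table on data already collected. No measurement, visit or protocol procedure changes.
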